APPENDIX

1. Amendments to the Protocol	12
2. Amendments to the Statistical Analysis Plan	13

PROTOCOL Version 1.3 (See Table of Amendments)

Multi-Center Randomized Controlled Trial of Refeeding in Anorexia Nervosa

1. Introduction

Current recommendations to guide the clinical care of AN patients hospitalized with medical instability due to malnutrition are based solely on retrospective or observational studies and/or clinical experience. No studies to date have prospectively tested high calorie refeeding (HCR) and the long-term impact on recovery is unknown. Consensus has developed over recent decades that patient safety can only be guaranteed using low calorie refeeding (LCR). The entrenchment of clinical practice without supporting evidence is a widely recognized dilemma in healthcare. While RCTs are considered the “gold standard” to establish evidence-based medicine, until recently there was insufficient data to propose such a study of refeeding in AN. We now have preliminary findings to indicate that LCR might be too cautious and that HCR appears feasible and may improve long-term recovery. Thus, we are poised to compare these two treatments in a parallel, randomized fashion.

2. Study Design

The purpose of this multi-center randomized controlled trial is to compare LCR vs. HCR refeeding strategies for hospitalized adolescents with AN. Participants will be recruited upon hospital admission at two centers (UCSF and Stanford) to maximize sample size, and randomly assigned 1:1 within site to one of the two strategies. A total of 120 participants age 12-24 yrs who meet DSM-5 diagnostic criteria for AN and atypical AN and present as medically unstable due to malnutrition will be enrolled. Treatments will not be blinded, since both the patients and clinicians who work with this population are highly skilled at estimating kcal and would be able to determine their group assignment by simply viewing the meal trays. In addition, target kcal will be reached faster in HCR and this would be apparent on physician orders. The proposed study is powered to detect a meaningful difference in clinical remission (Aim 1A).

2.1. Study Population

- a. **Inclusion/Exclusion:** Adolescents hospitalized for medical instability secondary to malnutrition will be eligible as follows. **Inclusion criteria:** diagnosis of AN, atypical AN, age 12-24 years, no hospital admissions for the previous six months, and meet hospitalization criteria (daytime HR < 50 bpm or night time HR < 45 bpm, BP <90/45 mmHg, temperature < 35.6° C or orthostasis defined by increase in HR > 35 bpm or decrease in systolic BP > 20 mmHg from lying to standing). **Exclusion criteria:** diagnosis of bulimia nervosa [DSM-5], currently in remission (as defined by weight and EDE-Q score per Aim 1), admission for food refusal without malnutrition, current pregnancy, chronic disease (e.g. immune/endocrine disorders, pulmonary, cardiac, or renal disease), current suicidality or psychosis.
- b. **Participant recruitment and consent:** Participants and their parents will sign assent (for those < 18 yr) and consent, respectively within 24 hr of hospitalization. This may occur in the clinic when they are deemed medically unstable and waiting transfer to the hospital or in the hospital if admitted directly. Consent will include permission to review all medical records, to review hospital billing data, and to contact for future research projects. If a participant turns 18 yr while enrolled, s/he will be reconsented. Participants 18 years of age and older are able to consent themselves; thus we will request verbal consent from their parents to complete parent surveys.

2.2. Randomization

Participants will be stratified by site and randomly assigned 1:1 to the two intervention strategies within 24 hr of hospital admission. The Data Coordination Center (DCC) will provide a secure unpredictable allocation sequence (e.g. A B B A ...) which will be programmed into a secure electronic study tracking system for assignment of each accrued participant. The sequences will be generated using block size of two to four to maximize balance between arms throughout accrual while ensuring the sequences remain unpredictable. As patients consent to study participation, clinical-research staff will assign the next available study ID number in sequence, identify the allocated intervention arm, and inform participants and their families of the assignment. In turn, the clinical research staff will provide the linked study ID number and Medical Record Number to the DCC, which will store this Personal Health Information in a HIPAA-compliant manner along with the intervention assignment.

3. Study Procedures

3.1. Treatment and Follow-up

- a. Study groups: Upon randomization, the Lower Calorie Refeeding (LCR) group will begin with 1400 kcal per day; Higher Calorie Refeeding (HCR) group will commence at 2000 kcal. Given our previous findings, recognition of the so-called underfeeding syndrome and recent clinical experience, we will not test a 1200 calorie diet even though it is still currently recommended. Our previous studies have adequately demonstrated that a 1200 kcal diet produces initial weight loss and therefore do not feel it is ethical to assign participants to this treatment. We chose 1400 kcal to start because in our previously study of LCR, weight loss ceased on day 3 in hospital when diets averaging 1411(299) kcal were prescribed. Diet prescriptions will increase by 200 kcal every other day in LCR and 200 kcal per day in HCR until a target level is reached. Target kcal are calculated upon admission as percent of energy needs using Estimated Energy Requirement (EER) equations from the Institute of Medicine. These equations are used clinically to set goals for caloric advancement although they are known to underestimate energy needs in patients with anorexia. Therefore, we maximize these estimations by using target weight corresponding to the mBMI for age and sex (rather than current weight), a moderate activity factor of 1.2-1.3 (despite bed rest), and additional 500 kcal (if current weight < the MBMI).
- b. Intervention (refeeding protocols): During hospitalization, participants will follow a meal-based refeeding protocol that calls for eating three meals and three snacks per day, served on trays at the bedside, in the presence of 'Room Sitters'. The calorie level of the diet will be prescribed by the physicians per study protocol and the meals will be prepared by hospital foodservice. The study PI ([name]) will work with the Research Registered Dietitian (RD) and nutrition staff at both sites to ensure that menu selections fit the general macronutrient distribution of 30-40% fat, 15-25% protein and 35-55% carbohydrate. Menus will be continually analyzed (Software v.17.9.5, Computrition, Inc., Chatsworth, CA) to ensure conformance to this distribution as menu items are added or change over time. Dietetic Technicians will keep daily calorie counts, per Standard of Care (SOC), showing actual kcal consumed from food and formula.

A high energy liquid supplement ("formula") providing 1.5 kcal per mL (360 kcal per 240 mL can) will be used orally as needed to replace kcal refused in meals or snacks per a standard calorie replacement protocol. We previously reported a greater than 98% concordance between kcal prescribed and actual kcal ingested using this method, as well as an equal proportion of kcal intake from formula in LCR and HCR groups. This finding supports our clinical observation that HCR meals can be completed without additional reliance on drinking formula. However, most AN patients do experience discomfort during refeeding and therefore all participants will receive SOC meal support including emotional support and techniques such as distraction. All beverages will be weighed and measured before placement on the tray, with a 1.5 L per day free water restriction. Room sitters will observe intake of all meals/snacks and remain in the room for 45 min afterwards.

c. Monitoring of electrolytes: Blood for electrolytes will be obtained between 5 and 7 am every 24hr for the first 7 days and more frequently if needed. Since the risk of refeeding decreases after the first week, electrolytes will be monitored every other day starting on day 8 unless there is continued evidence of abnormalities.

d. Correction of electrolyte abnormalities: Electrolyte abnormalities (serum phosphorus < 3 mg/dL, magnesium ≤ 1.7 mg/dL, or potassium < 3.5 mEq/L) will be corrected with a standardized protocol for both sites. Patients with hypophosphatemia will be treated with sodium potassium phosphate, 250 mg per packet (8 mmol phosphorus, 7.1 mEq potassium), one packet three times a day by mouth for a serum phosphorus between 2.5 and 2.9 mg/dL, two packets (500 mg) three times a day for a serum phosphorus of 2.0 - 2.5 mg/dL, and if serum phosphorus is < 2.0 mg/dL then intravenous sodium potassium phosphorus will be initiated at a dose of 0.24 mmol/kg (max of 15 mmol per dose). The PICU will be contacted and labs will be rechecked STAT 4 hours after the infusion is completed. Those with hypomagnesemia will be prescribed magnesium oxide (150 mg elemental Mg per tablet), one tablet three times a day by mouth for a serum magnesium between 1.3-1.7 mg/dL; two tablets three times a day by mouth for a serum magnesium between 1.0-1.2 mg/dL. In the case of serum magnesium below 1.0 mg/dL, the PICU will be called for possible transfer, and intravenous magnesium sulfate will be started at a dose of 50 mg/kg (max of 2 grams per dose). Labs will be rechecked STAT 2 hours after infusion completed: If repeat serum mag still < 1.0 mg/dL, repeat same dose of magnesium sulfate IV; If repeat serum mag > 1.0, begin PO Mag, at PO dose indicated above. Those with hypokalemia will be prescribed extended release potassium chloride by mouth, 20 mEq for a serum potassium of 3.1-3.4 mmol/L; and 40 mEq for a serum potassium of 2.5-3.0 mmol/L. For a serum potassium between 2.2 - 2.5 mmol/L, 40 mEq extended release potassium chloride will be given STAT and the PICU will be called for possible transfer. Labs will be rechecked in 4 hours (peak) and 12 hours (estimated nadir). For any serum value of potassium < 2.2 mmol/L, intravenous potassium chloride will be initiated and PICU will be called for transfer. Declining electrolyte levels that are in the normal range will not be treated. Participants will also receive a SOC supplement regimen including 500mg elemental calcium with vitamin D twice per day and an adult multivitamin with minerals once per day.

e. Study time points: Participants will be followed prospectively in hospital with daily measures of calorie and supplement intake and weight from admission through discharge. Patients will be discharged when medically stable, with the primary criterion of heart rate ≥ 45 bpm for least 24 hr. Full medical stability defined as HR ≥ 45 bpm for 24 hrs, temperature ≥ 35.6°C for 24 hrs, ≥ 75% of mBMI, BP ≥ 90/45 mmHg for 24 hrs or if systolic BP < 90 then asymptomatic and all else stable, orthostatic change in HR ≤ 35 bpm or if > 35 then asymptomatic and all else stable; and orthostatic change in SBP ≤ 20 mmHg or if > 20 then asymptomatic and all else stable.

Timing of Procedures: Table 1

	INPATIENT			OUTPATIENT FOLLOW---UP				
	Admit	Daily	DC*	10 dy	1 Mo	3 Mo	6 Mo	12 Mo
MEDICINE/NURSING PROCEDURES								
Weight	SOC	SOC	SOC	X	X	X	X	X
Height	SOC			X	X	X	X	X
Vital Signs	SOC	SOC	SOC	X	X	X	X	X
Electrolyte monitoring ¥	SOC	X	SOC					
NUTRITION PROCEDURES								
24---hr food recall	X			X	X	X	X	X
QUESTIONNAIRE ADMINISTRATION								
EDE-Q	X		X		X	X	X	X
HCUMS survey				X	X	X	X	X
Demogr & Eating Disorder	X							

Follow-up form				X	X	X	X	X
----------------	--	--	--	---	---	---	---	---

* DC = discharge; SOC = Standard Of Care; Rnd = Randomization; ¥ SOC is every other day; we will monitor daily as part of Aim 2.

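### Protocol 3.1.d puts phosphorus 2.5 mg/dL in two dose tiers and potassium 2.5 mmol/L in both the routine and the urgent tier

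*Combined protocol and SAP*

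**What the plan says.** Section 3.1.d of the protocol (Correction of electrolyte abnormalities) says that low phosphorus, magnesium and potassium "will be corrected with a standardized protocol for both sites".

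- **Phosphorus, upper oral tier:** "one packet three times a day by mouth for a serum phosphorus between 2.5 and 2.9 mg/dL".
- **Phosphorus, lower oral tier:** "two packets (500 mg) three times a day for a serum phosphorus of 2.0 - 2.5 mg/dL". Intravenous treatment starts below 2.0 mg/dL.
- **Potassium, routine tier:** "40 mEq for a serum potassium of 2.5-3.0 mmol/L", by mouth.
- **Potassium, urgent tier:** "For a serum potassium between 2.2 - 2.5 mmol/L, 40 mEq extended release potassium chloride will be given STAT", with a call to the PICU about possible transfer. The next sentence orders rechecks at 4 and 12 hours. Intravenous treatment starts below 2.2 mmol/L.
- **Magnesium, for comparison:** "one tablet three times a day by mouth for a serum magnesium between 1.3-1.7 mg/dL", then two tablets for 1.0-1.2 mg/dL, and intravenous treatment below 1.0 mg/dL.

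Section 3.1.c schedules a blood draw between 5 and 7 am each day for the first 7 days and lets staff draw sooner when they see a need. From day 8 the schedule is every other day unless abnormalities persist.

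**The concern.** The tiers are written to one decimal, so 2.5 is an ordinary reportable result, and for two electrolytes it meets two rules at once.

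For phosphorus the rules are incompatible, because a patient cannot receive both one and two packets at each dose. For potassium the dose agrees, but staff who follow the 2.5-3.0 tier as written could leave out the immediate dose, the PICU call and both rechecks. The next scheduled draw would then be the following morning's, in the first 7 days, unless someone chose to test earlier.

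At stake are patient safety at two specific readings and the commitment to treat alike at both sites. Participants are admitted because they are medically unstable, and electrolyte safety is Aim 2, so each reading should lead to one instruction.

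**Working it through.** **1. Count the boundaries.** All tiers are from section 3.1.d. Endpoints are taken as included, and results as reported to one decimal.

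| Electrolyte | Tiers, lowest first | Boundaries | Overlap |
|---|---|---|---|
| Phosphorus (mg/dL) | below 2.0; 2.0-2.5; 2.5-2.9 | 2.0; 2.5 | 2.5 |
| Magnesium (mg/dL) | below 1.0; 1.0-1.2; 1.3-1.7 | 1.0; 1.2/1.3 | none |
| Potassium (mmol/L) | below 2.2; 2.2-2.5; 2.5-3.0; 3.1-3.4 | 2.2; 2.5; 3.0/3.1 | 2.5 |

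That makes 2 + 2 + 3 = 7 boundaries, of which 2 overlap. Stepping through every value in units of 0.1 gives exactly two that match more than one tier (phosphorus 2.5 and potassium 2.5) and none below the treatment thresholds that matches no tier.

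**2. Test whether excluding endpoints rescues the text.** The word *between* introduces the upper phosphorus tier and the urgent potassium tier. Reading it as excluding the endpoints would settle both values at 2.5. The same reading would leave other values without an instruction:

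- Phosphorus 2.9 is abnormal (below 3) but would have no dose.
- Magnesium 1.7 is abnormal (at or below 1.7) but would have no dose.
- Potassium 2.2 would be outside the urgent tier and also outside the intravenous tier, which starts below 2.2.

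So the endpoints have to be included for the section to work, and including them creates the overlap.

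**3. Size at phosphorus 2.5.** Each packet holds 250 mg, 8 mmol phosphorus and 7.1 mEq potassium. Daily amount = packets per dose × 3 doses × content per packet.

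| | One packet (3 per day) | Two packets (6 per day) | Difference |
|---|---|---|---|
| Dose | 3 × 250 = 750 mg | 6 × 250 = 1500 mg | 750 mg |
| Phosphorus | 3 × 8 = 24 mmol | 6 × 8 = 48 mmol | 24 mmol |
| Potassium | 3 × 7.1 = 21.3 mEq | 6 × 7.1 = 42.6 mEq | 21.3 mEq |

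The daily dose differs by a factor of two. Both options are oral and neither involves escalation. In the first 7 days the tier can be revised at the next daily draw.

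**4. Size at potassium 2.5.** The dose is 40 mEq of extended release potassium chloride under either tier, a difference of 0. What differs is the timing of the dose, the PICU call and the two rechecks.

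**5. Effect on Aim 2.** SAP section 2.2 counts hypophosphatemia below 3 mg/dL and hypokalemia below 3.5 mEq/L. A reading of 2.5 is below both cut-offs, and either tier counts as supplementation. The classification of that reading and the patient's supplemented status are therefore the same under both rules.

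**The case against.** The strongest reply is that little depends on this.

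- **Potassium is not a true contradiction.** A clinician who does everything that applies at 2.5 gives 40 mEq at once, calls the PICU and rechecks, and so complies with both tiers. That is correct, and it is why the urgent tier is the right home for 2.5. It does not help staff who read only the 2.5-3.0 tier, which is also compliant on its face.
- **Phosphorus is one value between adjacent oral tiers.** Neither dose is shown to be unsafe, and Amendment 3 in Appendix Table 2 reports that electrolyte abnormalities proved rare. This stands, and it limits the point to a minor one.
- **Randomization is stratified by site, so a site's habit at 2.5 would apply to both arms.** This also stands. A consistent site habit would not by itself bias the comparison of arms.
- **The possible effect on later Aim 2 outcomes is not strictly nil.** An extra 21.3 mEq potassium per day could in principle affect a later potassium result, and the phosphorus dose could affect time to nadir. This is fair. The documents do not allow the effect to be quantified, and it is probably negligible.
- **The inpatient phase may be over.** Appendix Table 2 lists the locking of the short-term database, and the last date in that row is 07/31/2019. This affects what the correction is useful for, not whether the text overlaps.

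**Conclusion.** The concern holds, as a minor one. Section 3.1.d gives two incompatible doses at phosphorus 2.5 mg/dL (a difference of 24 mmol phosphorus and 21.3 mEq potassium for each full day on the tier). At potassium 2.5 mmol/L it leaves open whether the urgent steps apply. No other section resolves either value.

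The conclusion assumes included endpoints, which the rest of the section requires, and reporting to one decimal, as the tiers are written. The number of participants affected cannot be derived from the documents and is probably small. The sample size and planned analyses are unaffected.

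**What to change.** Make the two pairs of tiers non-overlapping at one decimal, as the other five boundaries already are.

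- **Potassium:** 2.2-2.5 mmol/L urgent (40 mEq at once, PICU call, rechecks at 4 and 12 hours); 2.6-3.0 mmol/L routine oral 40 mEq. At 2.5 this satisfies both current instructions. The cost is one call and two blood draws for a patient with that reading.
- **Phosphorus:** 2.0-2.4 mg/dL two packets and 2.5-2.9 mg/dL one packet, three times a day. If the clinical leads prefer the higher dose at 2.5, use 2.0-2.5 and 2.6-2.9 instead, which adds 24 mmol phosphorus and 21.3 mEq potassium per day at that value. Either works if both sites apply it alike.

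While inpatients are still being treated, this is a change of a few words submitted to the IRB as a protocol amendment. There is a precedent: Appendix Table 1 lists a change to electrolyte replacement under version 1.1, which the IRB approved. If inpatient treatment has ended, the sponsor can state how each site handled 2.5 and correct the tiers for any reuse of the protocol. Sample size, data collection and analysis do not change.

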3.2. Data Collection

Other than the treatment we are testing (HCR vs. LCR), patients will receive SOC in the hospital. Thus, as shown in **Table 1**, the vast majority of procedures in hospital are SOC. Follow-up visits, on the other hand, are for the purpose of collecting data and will be scheduled at the designated time points.

- a. **Baseline data collection:** The following covariates will be collected upon admission, prior to randomization.
 - (1) Demographics and eating disorder history: an intake form will be self-administered (with study coordinator as proctor, 15 min) to assess: highest body weight, lowest body, date of onset (to calculate length of illness and rapidity of weight loss), family history of eating disorder, self-reported race/ethnicity, maternal education and zipcode (to indicate socioeconomic status), date of birth.
 - (2) Eating Disorder Examination-Questionnaire (EDE-Q): is a standardized research interview that measures eating disorders psychopathology. [name] (co-I, UCSF) has used this tool extensively in RCTs examining psychotherapeutic modalities and long-term recovery in AN and BN and to categorize lower and higher risk study participants. He will oversee the psychological aspects of this study, including the EDE-Q.
 - (3) Food recall: dietary intake for the day prior to hospital admission will be assessed with a 24-hr food recall by the Research RD and analyzed via Nutrition Data System for Research (NDS-R) for total kcal and macronutrient profile. Dietary Density (DDS) and Variety Scores (DVS) will be calculated since acceptance of more energy dense and variety of foods in hospital has been shown to predict recovery at 8 mo.
 - (4) Severity of illness: %mBMI and HR on admission
 - (5) Health Care Utilization and Missed School (HCUMS) Survey: This proctored interview draws from established tools to assess cost, and has been tailored for AN and integrated with the follow-up form (above). In addition to "other care", it assesses health care utilization in the 6 months prior to admission including medications, physician visits, dental visits, ER visits and laboratory testing. It will be administered by trained research staff, who will document parent- and participant-reported care, supplemented with dates, doses, and other details available in the medical record.

b. Data collection daily in Hospital:

- (1) SOC in hospital: Participants will be followed daily in hospital. Consistent with SOC for these patients, night time HR will be assessed with continuous cardiac monitoring throughout hospital stay, temperature will be measured orally and BP will be measured every 4-8 hr. Postural changes will be assessed with supine measurements (after 5 min), followed by standing measurements (after 2 min). When multiple vital signs measures are taken per protocol during one hospital day or one outpatient clinic visit, the most deviant value (lowest HR, lowest BP, greatest increase in HR and greatest decrease in BP on orthostatic changes, lowest Temp) will be recorded. Weight is measured every morning upon waking after voiding on an electronic scale, with the subject wearing only a hospital gown. Height will be measured within 24 hours of admission with wall-mounted stadiometer. Electrolytes will be monitored per SOC as described above in 3.1.c.
- (2) Study in hospital: Participants at both sites will complete the questionnaires above.
- c. **Data collection during follow-up:** Participants will return for five study follow-up visits through 12

months post-discharge and complete the following procedures:

- (1) Anthropometrics and vital signs: Height, weight and vital signs will be measured according to the in-hospital protocol by trained medical staff with standard equipment. Vital sign measures will be taken after a 20-min rest to minimize the influence of activity required to attend the visit (e.g. walk from car). After resting, vital signs will be measured in the research center with standard, calibrated equipment and with postural changes according to the procedure above. Data will be entered directly into the electronic data capture system with fillable and constrained sections for anthropometric measures and vital signs to minimize error.
- (2) Food recall: dietary intake for one full day during the week of each follow-up visit will be assessed with a 24-hr food recall by the Research Dietitian.
- (3) HCUMS Survey: As described above, this proctored survey will assess utilization of health care such as re-hospitalizations since the time of the study-related hospitalization, participation in eating disorder treatment programs, medications, missed school, missed work, and other direct and indirect costs associated with eating disorder care since the time of each prior follow-up visit. The HCUMS will document medications pertinent to recovery measures (menses and psychopathology), including medications, current mental health care, other medical and psychological/psychiatric care ("other care") outside of our medical centers (e.g. residential care, psychiatric hospitalization). Psychotherapy modality and adherence may be important prognostic covariates of long-term outcomes in this open follow-up study.

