3.3. Safety

This study begins with a hospitalization as per SOC for patients who are medically unstable with malnutrition secondary to AN. Patients will be admitted to the adolescent medicine service if they are deemed medically unstable per published criteria. Once admitted, patients will be eligible for study enrollment. The treatment (HCR or LCR) is limited to the hospital stay. Aside from the questionnaires at both sites and daily (instead of every other day) electrolyte monitoring, all hospital procedures are consistent with SOC. After discharge, participants will be followed openly. They are required to be under a physician's care to ensure medical stability but not required to receive that care from us (however many do). Many patients have a psychiatrist to manage psychiatric co-morbidities such as anxiety and depression. If they receive care or hospitalization elsewhere they can still continue in the study and we will collect that with our follow-up form.

- a. Prospective monitoring of AEs: Aim 2 specifies three electrolyte abnormalities that will be monitored prospectively in all participants and documented as described in **3.1.c.&d.**: hypophosphatemia (<3 mg/dL), 2B) hypomagnesaemia (≤ 1.7 mg/dL), and 2C) hypokalemia (<3.5 mEq/L).
- b. Data and Safety Monitoring Board (DSMB): As a multi-center clinical trial comparing treatments, the proposed study is required to have a DSMB according to the NICHD policy for clinical research monitoring. The purpose of the DSMB is to ensure the safety of participants and validity of the trial. We will draft a DSM Plan using the NICHD template.

STATISTICAL ANALYSIS PLAN (most recent change May 26, 2019)

Multi-Center Randomized Controlled Trial of Refeeding in Anorexia Nervosa

1. Aims and Objectives

Our study has three main aims. We will compare:

AIM 1: Efficacy of LCR vs. HCR. We hypothesize that LCR and HCR will differ by *achievement and maintenance of* (1A) clinical remission during 12 mo follow-up, defined by achievement of both-(i) weight \geq 95% median BMI (MBMI) for age and sex, and (ii) Eating Disorder Examination-Questionnaire (EDE-Q) global score within 1 SD of clinical norm, and (1B) medical stability during initial hospitalization, defined by published vital sign thresholds.

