2.2. Outcomes

The primary analysis of the study adopts a modified intent-to-treat (mITT) approach to compare outcomes between randomized HCR and LCR participants who received treatment for at least one day. Patients who are ineligible post randomization, provide no assent after parent's consent, or withdraw before receiving any treatment, will not be included in the mITT analysis for reasons of data unavailability, ethics and clinical relevance. Sensitivity analyses will be conducted to check that 1) withdrawal patients are not different from patients in both groups included in mITT in baseline covariates; and 2) including withdrawal patients in the analyses will not change results and conclusion of mITT analyses. The sensitivity analyses will provide us

reassurance of mITT results.

Aim 1A: Primary (long-term) efficacy outcome. A (generalized) linear mixed-effects regression model (GLMM) will compare study arms with respect to achievement and maintenance of clinical remission. Clinical remission is defined as the combination of mBMI and EDE-Q score at mo 1,3,6,12 (separate analyses below) and measured at 1, 3, 6, and 12 months as 1) clinically remitted (yes or no) and 2) weight recovered (percent of mBMI). The models will include time, treatment group, time*treatment group interaction, and unbalanced baseline covariates if any as fixed effects, while sites and patients will be included as random effects to account for the correlation due to clustering. The time*treatment group interaction provides mITT effect of HCR compared to LCR on clinical remission over time. The average remission rates and scores and their 95% confidence intervals (CIs) will be estimated from the model. GLMM accounts for the fluctuating nature of mBMI and EDE-Q in AN and uses all available data with missing at random assumption, instead of a stronger assumption of missing completely at random required in other models. Aim 1 models will be supplemented with secondary analyses: (i) potential moderators at baseline (included in regression models as main effects and interactions with period and time), may include DSM-5 criteria and EDE-Q thresholds of risk and (ii) potential mediators at follow-up (included as time-dependent covariates), may include food recall (DDS and DVS), healthcare utilization, or incidence of AEs. In addition, separate mixed-effects models will analyze continuous versions of mBMI and EDE-Q to describe longitudinal trajectories.

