2.3. Power and Sample-size Considerations

Aim 1. Based on studies of AN remission, **Table 2.A** shows that with $N=60$ per arm we have 80% power on 2-sided 0.05-level test to detect a 20% difference (8% vs. 28%) if data were cross-sectional ($\rho=1$). Our longitudinal data will allow detection of smaller effects, especially if the correlation among outcomes is low ($\rho < 0.8$). We anticipate 85% retention and non-differential dropout by arm. Since **time to medical stability** is also expected to differ by at least 12% (**Table 2.B.**), we will be adequately powered for Aim 1B.

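### SAP 2.2 offers EDE-Q risk thresholds, with no cut-points, as a possible moderator of Aim 1A; the continuous baseline score would keep more information and leave no cut to choose

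*Combined protocol and SAP*

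**What the plan says.** SAP 2.2 (Outcomes, Aim 1A) supplements the Aim 1 models with secondary analyses of potential baseline moderators, which "may include DSM-5 criteria and EDE-Q thresholds of risk". These enter as main effects and as interactions with period and with time; an interaction with treatment group is not named. Nothing states how many thresholds there are, where they lie, or what share of patients would fall in each group.

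The underlying measure is a score. SAP section 1 defines remission partly by "Eating Disorder Examination-Questionnaire (EDE-Q) global score within 1 SD of clinical norm". Protocol 3.2.a places the EDE-Q in the baseline list, introduced by "The following covariates will be collected upon admission, prior to randomization". SAP 2.2 also plans models of continuous EDE-Q, but these describe the outcome over follow-up, not the baseline moderator.

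Protocol 3.2.a(2) contains the phrase "to categorize lower and higher risk study participants". Its sentence concerns how a co-investigator has used the instrument in previous trials; it is not an analysis rule for this one.

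**The concern.** A moderator analysis asks whether the difference between HCR and LCR depends on the level of eating-disorder psychopathology at admission. Grouping the score by thresholds treats everyone within a group as alike, and treats two patients just either side of a cut as different. That discards information in an interaction test, which is usually weak in a trial of this size.

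The missing cut-points are a separate problem. A subgroup finding can appear or vanish with the choice of cut. Treatment is open (Protocol section 2), and the SAP amendment table records that in-hospital outcomes could be analysed by arm ahead of the long-term ones. A threshold not fixed in the SAP could therefore be chosen with arm-level data in view. Nothing in the documents says that this was done or intended; a continuous moderator removes the question.

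**Working it through.** **Inputs from the documents**
- Sample size: "A total of 120 participants age 12-24 yrs", "randomly assigned 1:1 within site to one of the two strategies", so 60 per arm (Protocol section 2).
- Retention: "We anticipate 85% retention and non-differential dropout by arm" (SAP 2.3), so 0.85 × 120 = 102 at 12 months.
- Planned power: "we have 80% power on 2-sided 0.05-level test to detect a 20% difference (8% vs. 28"%) (SAP 2.3).

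**Assumptions, not in the documents:** the number and position of the cuts, the shape of the score, and a linear moderating effect.

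**1. The plan's own figure.** It refers to the comparison of arms, not to a moderator. With a pooled normal approximation, n = 60 per arm and mean rate 0.18:
- null SE = √(2 × 0.18 × 0.82 / 60) = 0.0701
- alternative SE = √((0.08 × 0.92 + 0.28 × 0.72) / 60) = 0.0677
- power = Φ((0.20 − 1.96 × 0.0701) / 0.0677) = 82.2%

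Fisher's exact test gives 77.1% and a logistic Wald test 81.0%, so the stated 80% is reasonable. The moderator question does not touch it.

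**2. Information kept after grouping a normal score.** This is the squared correlation between the score and its grouped form. For two groups with a share p on one side of cut c, it is φ(c)² / [p(1 − p)].
- Median: 0.3989² / 0.25 = 0.637
- 20/80: 0.2800² / 0.16 = 0.490

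For k groups it is the sum over groups of (difference in φ at the two boundaries)² / p_k.
- Tertiles: 2 × 0.3636² / (1/3) = 0.793

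| Grouping | Kept | Lost | 120 act like |
|---|---|---|---|
| Two, median | 63.7% | 36.3% | 76 |
| Two, 30/70 | 57.6% | 42.4% | 69 |
| Two, 20/80 | 49.0% | 51.0% | 59 |
| Two, 10/90 | 34.2% | 65.8% | 41 |
| Three, tertiles | 79.3% | 20.7% | 95 |
| Three, 27/46/27 | 81.0% | 19.0% | 97 |
| Four, equal | 86.1% | 13.9% | 103 |

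The fraction lost does not depend on sample size. With 102 retained, a median split acts like 102 × 0.637 = 65.

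**3. Sensitivity to shape.** With bounded, non-normal scores of several assumed shapes, a two-group median split loses 22% to 35%. The 36% minimum therefore belongs to the normal case.

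**4. Illustrative power.** Suppose the interaction has 80% power on the continuous score. After grouping, power = Φ((1.960 + 0.842) × √kept − 1.960).
- Median: Φ(2.802 × 0.798 − 1.960) = 61%
- 30/70: 57%
- 20/80: Φ(2.802 × 0.700 − 1.960) = 50%

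A simulation with 120 patients, a continuous outcome and an arm-by-moderator linear model (5,000 trials per setting) gave about 79% on the continuous score, against 58%, 54% and 47%. This checks the formula; it does not model the repeated binary remission outcome.

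**The case against.** The strongest reply is that the plan commits to very little. The wording is permissive, the analysis is secondary, and the continuous score is not ruled out. A reader might infer from Protocol 3.2.a(2) that this trial sorts patients into two risk groups, and hence that a third or more of the information is bound to be lost. The documents do not support that. The sentence reports past use in other trials, and SAP 2.2 speaks of thresholds in the plural, which could mean three or more groups. The 36% figure is conditional, and with more groups or a non-normal score the loss can be smaller.

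The 80% starting power is also arbitrary. From a starting power of 20%, the same formula gives about 14% after a median split, a fall of about 6 points rather than 19.

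Thresholds have a clinical rationale too: remission itself uses an EDE-Q threshold, and grouped results are easy to read. A continuous linear term carries its own assumption, and events may be too few for a rich check of it. At the planning rates, 60 × 0.08 + 60 × 0.28 = 21.6 patients would be in remission at a visit before dropout.

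All of this stands as a limit on the claim. It does not remove the point: thresholds are the only form of EDE-Q moderator that the SAP names, and none is defined. The wish for readable groups can be met from a continuous model.

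**Conclusion.** The point holds as a minor, conditional one. SAP 2.2 names baseline EDE-Q as a possible moderator only in threshold form and without cut-points, when the score itself is available. Grouping costs some information whenever the moderating effect is linear. For a roughly normal score, the loss is at least 36% with two groups, about 19-21% with three and about 14% with four equal groups. The documents do not say which case applies. The power figures of 61% and 50% illustrate the mechanism and are not estimates for this trial.

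A reader might also infer that the main efficacy result is weakened. It is not: the Aim 1A comparison of arms and its stated power do not depend on how a moderator is coded. Nor does the missing treatment interaction show that effect modification would go untested, since the term moderator implies one; it shows only that the model is not fully written down.

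**What to change.** In SAP 2.2, under the Aim 1A moderator analyses, state that the baseline EDE-Q global score enters as a continuous covariate with an explicit interaction with treatment group, extended to the time-by-treatment term where that is the effect being moderated. If risk groups are wanted for readers, report the fitted arm difference with its confidence interval at score values chosen in advance. Check linearity with one simple nonlinear term where the number of remissions allows. If thresholds are kept, state and justify their number and values before the 12-month analysis.

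The cost is one or two sentences and no new data. The small downside is the linearity assumption.
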